9.7 Overall Survival (OS)

Measured from the date of registration until death from any cause. OS for participants last known to be alive is censored at the date of last contact.

9.8 Treatment Discontinuation Reasons (See Section 6.6)

See Section 6.6.

10.0 STATISTICAL CONSIDERATIONS

10.1 Overview

This study will be conducted as a single institution, single arm study as described in Section 6.1. Patients with newly diagnosed ES-SCLC undergoing induction therapy with platinum- etoposide and ICI will be treated with bomedemstat maintenance therapy in combination with standard of care maintenance atezolizumab until disease progression, unacceptable toxicity, or other treatment discontinuation reason.

The primary objectives of this study are to evaluate the safety of bomedemstat in combination with maintenance atezolizumab and to evaluate the percentage of patients who are alive and free from disease progression at 6 months following the initiation of bomedemstat with atezolizumab.

10.2 Safety Evaluation

The DLT assessment period is 21 days from initiation of treatment. The first 6 eligible patients who receive at least one dose of bomedemstat and atezolizumab with at least 21 days of follow-up (safety analysis population) will be closely monitored for toxicities. If more than 2 patients experience DLTs (see Section 9.5), then the starting dose of bomedemstat for a given platelet count will be reduced by 0.1 mg. Otherwise, accrual will proceed as described in Section 10.3. If the dose is reduced, following 6 additional patients meeting the criteria to be assessed for DLTs, the same rules will apply (continue at dose if <3 patients with DLT and dose reduce by 0.1 mg if >2 with DLT).

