3.1.5 Administration

Appropriately trained personnel of the study site will provide instruction pertaining to bomedemstat administration. All bomedemstat doses will be self-administered by the patient off-site.

Patients should be instructed to:

1. Take their bomedemstat once daily, at night before bed at approximately the same time (suggest that patient select their dosing time with consideration given to fasting requirements).
2. Swallow their bomedemstat capsules whole, with a glass of water.

3. Take bomedemstat on an empty stomach (fast for 1 hour prior to and 30 minutes after dose).
Patients may have clear liquids prior to their dose and following study drug administration.
Patients may take other medications at the same time as bomedemstat.

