3.1.6 Missed Doses

Patients who do not take their bomedemstat dose at the usual required time should take it immediately upon noting that it was not taken; however, the patient should not take the dose more than 12 hours after the usual dosing time. If a patient misses a dose, they should not take two doses the following day, but should notify their study coordinator and continue with their normal daily dose the following day.

For a dosing hiatus due to a serious adverse event (SAE), please consult the Principal Investigator for guidance on dosing re-start. Patients who miss an extended number of bomedemstat doses or exhibit serial non-compliance with treatment may be removed from the study at the discretion of the Principal Investigator.

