9.5 Dose-limiting Toxicity (DLT) Definition

DLT to bomedemstat combined with atezolizumab is defined as the occurrence of any of the following toxicities by CTCAE 5.03 determined to be possibly, probably, or likely related to bomedemstat or atezolizumab occurring within 21 days of initiation of treatment. The specific events are:

1. Grade 4 non-hematologic toxicity (not laboratory).
2. Grade 3 non-hematologic toxicity (not laboratory) lasting >3 days despite optimal supportive care.
3. Any Grade 3 or Grade 4 non-hematologic laboratory value if:
 - a. Medical intervention is required to treat the patient, or
 - b. The abnormality leads to hospitalization
4. Thrombocytopenia leading to clinically significant sequelae (i.e., a clinically significant bleeding event or the need for prophylactic transfusions).

Note: Thrombocytopenia is defined for this purpose as a platelet count < 100x10³/mcL. A clinically significant bleeding event is defined as an event that is life-threatening, cannot be controlled, and/or results in hemodynamic instability. Prophylactic transfusion is defined as platelet transfusion in the setting of a platelet count of < 10x10³/mcL.

5. Febrile neutropenia.
6. Grade 5 toxicity.

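### Section 10.2 sets no minimum bomedemstat exposure for the six-patient DLT set: a non-toxic early stopper who stays in follow-up counts as DLT-free, and an early toxic death could be left out

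*Combined protocol and SAP*

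**What the plan says.** Section 6.1 leaves any change to the bomedemstat starting dose to the safety evaluation in Section 10.2. That section sets the window ("The DLT assessment period is 21 days from initiation of treatment") and defines the safety analysis population as "The first 6 eligible patients who receive at least one dose of bomedemstat and atezolizumab with at least 21 days of follow-up". The starting dose is reduced "If more than 2 patients experience DLTs", that is, at three or more of six. After a reduction, "following 6 additional patients meeting the criteria to be assessed for DLTs, the same rules will apply", so a second set is filled in the same way.

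Section 9.5 counts listed toxicities "occurring within 21 days of initiation of treatment" that are judged related to either drug. Grade 5 toxicity is on the list.

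Bomedemstat is taken daily, and Section 3.1.5 states: "All bomedemstat doses will be self-administered by the patient off-site". Section 3.1.6 says "Patients who miss an extended number of bomedemstat doses or exhibit serial non-compliance with treatment may be removed from the study", at the Principal Investigator's discretion, but does not say whether such a patient counts in the DLT set. Section 6.6.2 lists reasons for stopping that are not toxicity, such as noncompliance and intercurrent illness. Sections 6.6, 8.4.1 and 8.5.3.2 keep patients under observation after treatment stops, with a safety visit at about 30 days. No section sets a minimum share of the 21 daily doses for the DLT set or an explicit rule for replacing patients in it.

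**The concern.** The six-patient check is the plan's formal test of the starting dose. Safety is a primary objective, and Section 2.5 says that the strategy of adding LSD1 inhibition to checkpoint inhibition had not yet been tested in clinical trials. Section 2.7 describes the myelosuppression as dose-dependent and reversible when treatment stops. A patient who takes a few doses and stops for a reason unrelated to toxicity therefore says little about three weeks at the starting dose, yet occupies one of six places.

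The follow-up condition can also fail in the opposite case. A patient who dies of toxicity on, say, day 10 has had a DLT but has not had 21 days of follow-up. Both features push the DLT count down. What is at stake is a lower chance of triggering a reduction when one is warranted, with later patients then starting at the same dose.

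**Working it through.** **Step 1. Who fills a place under the current wording**

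| Patient (had both drugs) | Section 10.2 as written | What the check needs |
|---|---|---|
| Lost or removed before day 21, no DLT | Not among the six; next patient fills the place | Same |
| Stops bomedemstat early for a non-toxic reason, stays in follow-up | Counted, DLT-free | Replaced |
| Doses held or reduced for toxicity, followed to day 21 | Counted | Counted |
| Dies of toxicity before day 21 | Left out on a literal reading | Counted as a DLT |

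**Step 2. The plan's own figures.** The documents give no operating characteristics for the 3-of-6 rule, so there is none to reproduce. The one toxicity figure in Section 10.3 concerns all 34 patients: 1 − 0.9^34 = 0.972, matching the stated 97%. It is not affected by this point.

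**Step 3. Inputs.** From the documents: set size 6 and trigger of 3 or more. Assumed, because the documents do not give them: true DLT rate p of 20%, 40% or 50%; one of six under-exposed, with either no DLT risk or half the risk p.

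**Step 4. Six exposed patients.** P(X ≥ 3) = 1 − Σ(x = 0 to 2) C(6,x) p^x (1−p)^(6−x). At p = 0.40: 1 − (0.0467 + 0.1866 + 0.3110) = 0.456.

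**Step 5. One of six with no DLT risk.** All three DLTs must come from the other five. At p = 0.40: 1 − (0.0778 + 0.2592 + 0.3456) = 0.317.

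**Step 6. One of six at half risk.** P5(X ≥ 3) + P5(X = 2) × p/2, where P5 refers to the five exposed patients. At p = 0.40: 0.3174 + 0.3456 × 0.20 = 0.387.

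| True DLT rate | Six exposed | One with no risk | One at half risk |
|---|---|---|---|
| 20% | 9.9% | 5.8% | 7.8% |
| 40% | 45.6% | 31.7% | 38.7% |
| 50% | 65.6% | 50.0% | 57.8% |

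**Step 7. Averaging over how often early stops occur.** If each patient independently has probability u of a non-toxic, risk-free early stop, the per-patient DLT probability becomes p(1 − u). At p = 0.40:
- u = 5%: 0.40 × 0.95 = 0.38, and P(X ≥ 3) = 41.4%.
- u = 10%: 0.40 × 0.90 = 0.36, and P(X ≥ 3) = 37.3%.

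The chance that at least one of six stops early is 1 − 0.95^6 = 26.5% and 1 − 0.90^6 = 46.9% respectively.

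**Step 8. The excluded death.** Suppose three of six patients have DLTs and one of those is a toxic death before day 21. Left out on the literal reading, that patient takes the count from three to two, and the trigger is missed unless the next patient also has a DLT.

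**The case against.** The strongest reply is that replacement is partly built in. Because 21 days of follow-up are required, a patient who withdraws consent and leaves follow-up, or who is removed from the study under Section 3.1.6 before day 21, is not one of the six. That stands, and it confines the gap to patients who stop the drug but remain followed.

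Very early progression is also unlikely. Section 5.1 requires stable disease or better after induction and a life expectancy of at least 12 weeks, and the first scheduled on-treatment scan is at six weeks. This makes early stopping less frequent; it does not rule out noncompliance or intercurrent illness.

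An under-exposed patient is not necessarily free of DLT risk. Events related to atezolizumab count, bomedemstat is irreversible (Section 2.6), and its effects may outlast serum levels (Section 8.6.2). The zero-risk column is therefore an upper bound on the loss from one such patient, and the half-risk column is shown beside it. Nor do the documents point to a high DLT rate: Section 2.7 reports no dose-limiting toxicities in the myelofibrosis and essential thrombocythemia studies, though those were other diseases and the protocol does not describe atezolizumab being given in them.

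Finally, harm from a missed trigger is limited. Cycle 1 has weekly blood counts, with holds and down-titration on Days 8 and 15. Sections 10.2.1 and 10.2.2 contain study-wide stopping rules, and Section 12.0 provides for weekly review. All of this stands as mitigation. None of it changes who is counted in the DLT denominator.

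**Conclusion.** The point holds in a limited form. Section 10.2 states a rule under which one dose of each drug plus 21 days of follow-up fills a place. That rule can count a barely exposed patient as DLT-free and, read literally, can omit an early toxic death. The first feature lowers the chance of meeting the trigger. At a 40% DLT rate, one such patient costs 45.6 − 38.7 = 6.9 percentage points at half risk and 45.6 − 31.7 = 13.9 at most. Averaged over a 5–10% early-stop probability with no DLT risk, the loss is about 4 to 8 points. At a 20% DLT rate, one risk-free patient costs 9.9 − 5.8 = 4.1 points. The DLT rates, early-stop rates and residual risks are all assumptions; no stated figure in the plan is wrong.

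A reader might infer more: that every early stopper is retained, that platelet suppression is cumulative so a short exposure carries no risk, or that patients would be left unprotected at an intolerable dose. The documents do not support these. Dropouts before day 21 are passed over, Section 2.7 says dose-dependent rather than cumulative, and the titration and stopping rules operate throughout. The 34-patient efficacy calculation is unaffected. This is a cheap improvement.

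**What to change.** In Section 10.2, define a DLT-evaluable patient as one who received study treatment and either:

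- has a DLT within 21 days, whatever the length of follow-up; or
- completes the 21 days having taken a minimum share of planned bomedemstat doses plus the Cycle 1 atezolizumab.

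The sponsor should set the share in advance. As an example, 75% of 21 is 15.75, so 16 doses; the documents do not dictate this value. Count doses held or reduced for toxicity under Sections 6.2 or 6.3 as taken, so that patients who tolerate the drug poorly are not discarded. Replace non-evaluable patients in the set with the next patient enrolled, and apply the same definition to any second set. Keep replaced patients in the primary endpoint analysis and in all toxicity tables.

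The cost is a short text change. Replacements come from the planned 34, so total accrual does not rise and no dosing rule changes. The downside is that the safety read may wait for one or two more patients.

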1.1 Primary Objectives

1. Evaluate the percentage of patients alive and progression-free six months after initiating maintenance therapy with bomedemstat and atezolizumab.
2. Evaluate the safety and tolerability of maintenance therapy with bomedemstat and atezolizumab.

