6.6.2 Other criteria for discontinuation of study treatment and/or withdrawal

An individual subject will not receive any further study treatment and will proceed to Off Treatment monitoring if any of the following occur in the subject in question:

1. The subject withdraws consent.
2. Unacceptable adverse events as defined in Section 6.3.

Note that encephalopathy of any grade is always considered an unacceptable adverse event (see Section 10.2.1).

3. Adverse event that, in the opinion of the investigator, contraindicates further dosing.
4. Subject noncompliance that, in the opinion of the investigator, warrants withdrawal, e.g., refusal to adhere to scheduled visits.
5. Subject is determined to have met one or more of the exclusion criteria for study participation at study entry and continuing investigational therapy might constitute a safety risk.
6. Intercurrent illness that prevents further administration of treatment.
7. Investigator's decision to withdraw the subject.
8. The subject has a confirmed positive serum pregnancy test.
9. Noncompliance with trial treatment or procedure requirements.
10. The subject is lost to follow-up.
11. Grade ≥ 3 infusion reaction.

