10.3 Sample Size Justification and Analysis Plans

The total accrual goal to this study is 34 eligible patients. Based on the IMPOWER133 study, we estimate that 35% of patients with ES-SCLC are alive and free from disease progression at 6 months after initiation of maintenance anti-PD(L)1 therapy. With 34 patients, this study design has 90% power to detect a 25% improvement in 6-month PFS rates (from 35 to 60%) using a 1-sided binomial test at the 5% level. The observation of 17 patients progression-free (i.e. alive without PD or symptomatic deterioration) at 6 months (a 50% rate) would be considered evidence to rule out a 35% 6-month PFS rate. With 34 patients, proportions can be estimated to within 17% with 95% confidence and any toxicity with at least 10% prevalence is likely to be observed with 97% confidence.

Additional analyses will evaluate proportions (such as toxicity or response rates within subgroups) accompanied by 95% confidence intervals. Distributions for time-to-event outcomes (PFS, OS) will be evaluated using the method of Kaplan-Meier. For point estimates at landmark times, the associated 95%

confidence interval (CI) will be calculated using Greenwood's formula and based on a log-log transformation applied on the survival function.

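### The six-patient DLT count in section 10.2 leaves out a dosed patient later found ineligible, and section 10.3 names no denominator for toxicity rates

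*Combined protocol and SAP*

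**What the plan says.** Safety is a primary objective. Section 1.1 lists it as "Evaluate the safety and tolerability of maintenance therapy with bomedemstat and atezolizumab".

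The DLT rule in 10.2 starts from "The first 6 eligible patients who receive at least one dose of bomedemstat and atezolizumab". The same sentence adds the follow-up condition and the label: "at least 21 days of follow-up (safety analysis population) will be closely monitored for toxicities". The decision rule follows: "If more than 2 patients experience DLTs", the starting dose is reduced; otherwise accrual goes on. After a reduction, six more patients who meet the same conditions are assessed under the same rule.

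Section 10.3 sets the size: "The total accrual goal to this study is 34 eligible patients". For 34 patients it then states that "proportions can be estimated to within 17% with 95% confidence" and that "any toxicity with at least 10% prevalence is likely to be observed with 97% confidence". It plans toxicity proportions with 95% confidence intervals but does not say over which patients. No section defines a set of all treated patients.

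Section 6.6.2 item 5 lists, among the reasons to stop study treatment, "Subject is determined to have met one or more of the exclusion criteria for study participation at study entry", where going on might be a safety risk. It does not say how such a patient is analysed. AE recording in 8.6 starts at Cycle 1 Day 1 for patients generally, and the two stopping rules in 10.2.1 and 10.2.2 apply without regard to eligibility.

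**The concern.** A DLT is informative about the regimen whether or not the patient should have been enrolled. Section 10.2 makes eligibility a condition of being counted, so a finding made after dosing can remove a DLT from the count that decides on the starting dose. The documents' other safety provisions have no such condition, which makes the DLT rule the odd one out.

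The follow-up condition has a similar effect. A patient who dies of toxicity or leaves because of it before day 21 does not have 21 days of follow-up, yet may have had exactly the event the rule is meant to catch.

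For the whole-study toxicity rates the problem is different and smaller. The population for a primary objective is left unstated, and the only set labelled for safety analysis is the six-patient one.

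**Working it through.** **The plan's own figures (10.3: n = 34, prevalence 10%).**
- Chance of seeing at least one case: 1 − (1 − 0.10)^34 = 0.972, stated as 97%.
- 95% half-width at a proportion of one half: 1.96 × √(0.25/34) = 0.168, stated as 17%.

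Both reproduce.

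**The DLT rule (10.2: six patients, trigger at more than 2).** The chance of a reduction is P(X ≥ 3) for X binomial with n = 6. The documents give no expected DLT rate, so a range is assumed:
- true DLT rate 10%: 0.016
- 20%: 0.099
- 30%: 0.256
- 40%: 0.456
- 50%: 0.656

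**What the eligibility condition does.** Suppose 3 of the first 6 treated patients have DLTs.
- Counting all six: 3 > 2, so the starting dose is reduced.
- One of the three is ruled ineligible before the count is settled. Five eligible patients remain, with 3 − 1 = 2 DLTs, and the seventh treated patient takes the sixth place.
- Replacement without a DLT: 2 is not more than 2, so accrual proceeds. Replacement with a DLT: 2 + 1 = 3, so the dose is reduced.

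With independent patients and a true DLT rate p, accrual proceeds in this situation with chance 1 − p: 90% at p = 10%, 70% at p = 30% and 50% at p = 50%.

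**The 21-day condition beside 9.5.** Section 9.5 counts related events within 21 days of starting treatment and lists Grade 5 toxicity among the DLTs. A toxic death on, say, day 10 meets 9.5, but the patient cannot reach the 21 days of follow-up in 10.2. Read literally, the event is a DLT in a patient who is not in the set. The two sections must be reconciled.

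**Toxicity rates with an all-treated denominator.** The documents give no number of treated but ineligible patients, so k = 1 to 3 beyond the 34 is assumed.
- Detection at 10% prevalence, 1 − 0.9^(34 + k): 97.5%, 97.7% and 98.0%, against 97.2%.
- Half-width: 16.6, 16.3 and 16.1 points, against 16.8.
- Example with 3 events in 34 eligible patients, 3/34 = 8.8% (95% CI 1.9 to 23.7). For k = 1 the all-treated rate lies between 3/35 = 8.6% and 4/35 = 11.4%. For k = 3 it lies between 3/37 = 8.1% and 6/37 = 16.2%.

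The sizing statements move by less than 1 point. An observed rate can move more if the extra patients had the event.

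**The case against.** **A fixed, eligible, fully followed six-patient set is a legitimate design choice.** It is, and six patients with a threshold of more than 2 need not change. But the protocol gives no reason for discarding a DLT in a dosed patient, and its other safety rules do not do so.

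**The case is rare and there are backstops.** Section 5.0 forbids eligibility waivers and 8.1.2 requires every criterion to be checked. The example needs an ineligible patient with a DLT among the first six when exactly two others also have one. Events in such a patient are still recorded and still count under 10.2.1 and 10.2.2. All of this stands and limits the size of the point. It does not repair the count in 10.2.

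**Counting more patients makes the rule stricter.** With a seventh patient counted against the same threshold, the trigger chance at a 30% DLT rate would rise from 0.256 to 0.353. That would be a different rule. It does not follow if the set stays at six.

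**Stronger readings that the documents do not support.**
- A reader might infer that ineligible patients are dropped from the toxicity rates. In 10.3 the word eligible qualifies only the accrual goal, and the denominator is unstated.
- A reader might set the 97% against 1 − 0.9^6 = 46.9% for the six-patient set. Section 10.3 ties the 97% to 34 patients, and nothing says that whole-study toxicity will be reported in six.
- A reader might suppose that ineligibility is usually uncovered because of a safety event, so that toxicity is biased downward. The documents give no frequency and no such link.
- A reader might take 1/34 = 2.9 points as the general effect of one exclusion. It is the largest case, 1/35 against 0/34. With 3 other events, leaving out a patient with the event moves the rate from 11.4% to 8.8%; leaving out one without it moves the rate from 8.6% to 8.8%.

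**Conclusion.** The concern holds for the DLT count. Section 10.2 states a rule that drops a DLT in a dosed patient later found ineligible, and one such patient can turn 3 counted DLTs into 2 and reverse the decision. In that situation the reversal stands with chance 1 − p, or 50% to 90% over assumed DLT rates of 50% down to 10%. How often the situation would arise cannot be derived from the documents. If eligibility findings are unrelated to DLTs, replacing such patients leaves the trigger chances as they are, so the harm lies in the individual case and in any link between the two.

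The 21-day condition adds a second gap, which conflicts with the inclusion of Grade 5 toxicity in 9.5.

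For the toxicity rates the defect is only an undefined denominator. The 97% and 17% figures are right and are hardly affected by 1 to 3 extra treated patients, which is an assumed range.

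**What to change.** **Section 10.2.** Replace the label with DLT-evaluable set. Define the set as the first 6 treated patients, regardless of later eligibility findings, who either complete 21 days of follow-up or have a DLT before then. Keep the size of six and the threshold of more than 2, and apply the same definition to the second six after a dose reduction. This also brings 10.2 into line with 9.5 for early deaths that meet the DLT definition.

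**Section 10.3.** State that toxicity proportions are reported in all patients who receive at least one dose of study treatment, regardless of later eligibility findings.

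**Cost.** This is a wording amendment that needs no extra recruitment. The toxicity denominator may slightly exceed 34, and the DLT set may include a patient outside the target population. Such patients can be flagged in the report.
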